## **8.0 STATISTICAL ANALYSIS PLAN**

### **8.1 Hypotheses**

Objectives and hypotheses of the study are stated in the Section 3.0.

### **8.2 Analysis endpoints**

#### **8.2.1 Primary Efficacy Endpoint(s):**

Overall responsive rate (ORR) [Time Frame: at each treatment cycle 1 to 35 (each cycle is 3 weeks)] - ORR is defined as the proportion of subjects in the analysis population who have a complete response (CR) or partial response (PR)

#### **8.2.2 Secondary Efficacy Endpoint(s):**

1. Disease Control Rate (DCR) [Time Frame: up until the first sign of progression through to study completion (2 years)] - DCR will be measured as CR, PR or stable disease (SD) at 6, 12 and 24 months
2. Progression-free Survival (PFS) [Time Frame: up until the first sign of progression through to study completion (2 years)] - PFS will be measured from the date of treatment commencement to the date of first progression at any site or date of death from any cause
3. Overall Survival (OS) [Time Frame: up until the first sign of progression through to study completion (2 years)] - OS will be measured from the date of treatment commencement to the date death from any cause
4. Duration of Response (DOR) [Time Frame: up until the first sign of progression through to study completion (2 years)] - DOR will be assessed on patients who responded to treatment and will be measured from the start of study medication until disease progression or death due to any cause, whichever occurs first, based on assessment per RECIST 1.1.

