Subject with confirmed APOBEC3B germline mutation will be given another informed consent form to participate in the main study.

The primary objective of the trial is to determine the efficacy of pembrolizumab in metastatic HER2-negative breast cancer subjects with APOBEC3B germline deletion polymorphism. Secondary objectives include progression-free survival (PFS), overall survival (OS) and response duration in this subject populations. The relationships of the germline variation, the associated molecular signatures, as well as other potential prognostic biomarkers with the study treatment will be explored as the exploratory objectives.

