#### **3.3 Secondary Objectives**

- 1) To estimate the disease control rate (DCR) i.e. complete response (CR), partial response (PR) or stable disease (SD) to the pembrolizumab treatment in metastatic HER2-negative breast cancer patients with germline APOBEC3B deletion polymorphism.
- 2) To estimate the progression free survival (PFS) to the pembrolizumab treatment in metastatic HER2-negative breast cancer patients with germline APOBEC3B deletion polymorphisms.
- 3) To estimate overall survival (OS) to the pembrolizumab treatment in metastatic HER2-negative breast cancer patients with germline APOBEC3B deletion polymorphisms.

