### 4.2.3 Rationale for Endpoints

#### 4.2.3.1 Efficacy Endpoints

**Primary Endpoint:** Overall response rate (ORR) at each treatment cycle 1 – 35 (each cycle is 3 weeks) based on RECIST 1.1. It is commonly used in clinical trials to evaluate cancer treatments for objective response in solid tumours. The observed effect is attributable directly to the drug, not the natural history of the disease. Its application in tumour progression measurement is well accepted by regulatory authorities.

**Secondary Endpoint:** Disease control rate (DCR, i.e. complete response (CR), partial response (PR) or stable disease (SD)) at 6, 12 and 24 months based on RECIST 1.1. For subjects who demonstrate CR, PR or SD, duration of response (DOR) is defined as the time from the start of study medication until the first sign of disease progression.

Progression Free Survival (PFS) measures the time from start of study medication until the first sign of disease progression based on RECIST 1.1 or death from any cause, whichever occurs first. It is a widely accepted endpoint in breast cancer Phase II clinical trials.

Overall Survival (OS) measures the date from study commencement to the date death from any cause. Patients alive or lost to follow up are censored. Overall survival as an endpoint is easily measured, unambiguous, objective and unaffected by the timing of assessment.

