**Table 1 Trial Treatment**

Drug	Dose/ Potency	Dose Frequency	Route of Administration	Regimen/ Treatment Period	Use
Pembrolizumab	200 mg	Q3W	IV infusion	Day 1 of each 3 week cycle	Experimental

Trial treatment should begin on the day of treatment allocation or within 3 days of treatment allocation.

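### Duration of response is timed from the start of study medication, which makes it PFS in responders, and Sections 8.2.2 and 4.2.3.1 disagree on who is counted and on death

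*Protocol*

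**What the plan says.** Section 8.2.2 lists DOR as the fourth secondary efficacy endpoint. It is assessed in patients who responded and "will be measured from the start of study medication until disease progression or death due to any cause", whichever is first, per RECIST 1.1. The same section states that "PFS will be measured from the date of treatment commencement to the date of first progression at any site or date of death"; here too, every death counts, whatever its cause.

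Section 4.2.3.1 defines both endpoints a second time. On DOR it says: "For subjects who demonstrate CR, PR or SD, duration of response (DOR) is defined as the time from the start of study medication" to the first sign of progression; death is not mentioned. On PFS it says that the endpoint "measures the time from start of study medication until the first sign of disease progression based on RECIST 1.1 or death from any cause".

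Section 8.2.1 counts only CR and PR as response for the primary endpoint. Sections 3.3 and 8.2.2 use CR, PR or SD for the disease control rate. Section 2.0 names response duration among the aims ("Secondary objectives include progression-free survival (PFS), overall survival (OS) and response duration in this subject populations"), while the numbered list in Section 3.3 contains only disease control rate, PFS and OS. Section 8.7.1 provides for Kaplan-Meier summaries of the secondary endpoints where appropriate.

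**The concern.** DOR should say how long a response lasts once it has been achieved. A clock that starts at first dose measures something else: time to response plus duration of response. That sum is the responder's PFS, so the endpoint adds nothing to PFS beyond selecting the responders. In a Kaplan-Meier summary no patient can have an event before her own response, so the start of the curve is event-free by construction.

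The second problem is that the protocol holds two definitions. Under Section 4.2.3.1 the result would describe everyone with disease control, including patients who never responded. The two sections also leave it unclear whether a death without progression is an event. No section says which definition prevails, so two analysts could report different populations and different event counts under the same label.

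This is a single-arm trial, so a reader is likely to set its DOR beside published figures such as those cited in Sections 4.2.1.1 and 4.2.1.2. A value inflated by time to response would mislead in any comparison with figures measured from response.

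**Working it through.** The protocol states no number for this endpoint, so there is no figure to reproduce. The check compares the definitions term by term and then sizes the difference.

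**Definitions side by side**

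| | DOR, 8.2.2 | PFS, 8.2.2 | DOR, 4.2.3.1 | PFS, 4.2.3.1 |
|---|---|---|---|---|
| Population | responders | not restricted | CR, PR or SD | not restricted |
| Start | start of study medication | treatment commencement | start of study medication | start of study medication |
| End | progression or death | progression or death | progression; death not named | progression or death |

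Start of study medication and treatment commencement are the same date: Section 4.2.3.1 uses the former for PFS and Section 8.2.2 the latter. The PFS wording about any site and the DOR wording about RECIST 1.1 do not separate the endpoints, because Section 4.2.3.1 ties PFS to RECIST 1.1 and Section 7.1.2.6.5 makes RECIST 1.1 the basis for the date of progression. I read responders in Section 8.2.2 as CR or PR, following Section 8.2.1.

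For each responder, therefore:

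DOR (8.2.2) = PFS = time to response + time from first response to progression or death.

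The excess over DOR measured from response is the time to response.

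**Size from the scan schedule**

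Inputs: first dose 0 to 3 days after allocation (Table 1: "Trial treatment should begin on the day of treatment allocation or within 3 days of treatment allocation"); first on-study scan 63 ± 7 days after allocation and further scans every 9 weeks ± 7 days in the first year (Section 7.1.2.6.2). One month is taken as 30.44 days.

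- First scheduled scan, minimum: 63 − 7 − 3 = 53 days = 7.6 weeks = 1.7 months.
- First scheduled scan, maximum: 63 + 7 − 0 = 70 days = 10.0 weeks = 2.3 months.
- Dosing on the allocation day, minimum: 63 − 7 = 56 days = 8.0 weeks = 1.8 months.
- Second scheduled scan, windows counted from allocation: 126 − 7 − 3 = 116 days to 126 + 7 = 133 days (3.8 to 4.4 months).
- Second scheduled scan, windows counted from the previous scan: 2 × 56 − 3 = 109 days to 2 × 70 = 140 days (3.6 to 4.6 months).

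The minima hold for scheduled scans only, because Section 7.1.2.6.2 allows more frequent imaging if clinically indicated.

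**Size from the protocol's cited evidence**

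Section 4.2.1.1 gives a median time to response of 17.9 weeks (range 7.3 to 32.4) in the phase 1b triple-negative study: 17.9 × 7 / 30.44 = 4.1 months. It also cites a median DOR of 6.3 months in cohort A of the phase II study. The protocol does not say from when that was measured; assume from response. With every responder shifted by the same amount:

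- response at week 9: 6.3 + 2.1 = 8.4 months (+33%);
- response at 17.9 weeks: 6.3 + 4.1 = 10.4 months (+65%).

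An illustrative simulation of 1,000,000 responders, with response first seen at week 9 or week 18 with equal chance and an exponential duration with median 6.3 months thereafter, gave medians of 6.3 months from response and 9.5 months under Section 8.2.2.

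None of this sizing applies to patients with SD under Section 4.2.3.1, who have no time to response.

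**The case against.** Section 4.2.3.1 is a rationale paragraph, while Section 8.0 is the statistical plan. An analyst would probably work from Section 8.2.2, where DOR is limited to responders. On that view the silence on death in Section 4.2.3.1 is an omission that Section 8.2.2 completes rather than an opposing rule, and only the inclusion of SD is a true contradiction. This is reasonable, but the protocol does not state the precedence. It also does not touch the first defect, because both sections start the clock at first dose.

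That shared start date can be called consistent and executable. It is; the fault is that the quantity it yields is PFS in responders under another name.

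Section 8.7.1 provides Kaplan-Meier only as appropriate and does not name DOR. That stands, so the remark about the event-free start of the curve holds if the method is applied to DOR.

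The strongest point is weight. DOR is descriptive and missing from the numbered objectives. The responders will be few: about 10 at a 25% rate in 40 evaluable patients (0.25 × 40), about 4 at 10%, and at most 5 if the trial stops at stage I for fewer than 6 responses. Response dates will be available, so the conventional quantity can still be derived. This lowers the priority but does not remove the error: an analyst who follows the written rule reports the wrong duration.

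**Conclusion.** The concern holds. As written in Section 8.2.2, DOR equals PFS in every responder and exceeds her duration of response by her time to response. The excess is 53 to 70 days for a response first seen on the first scheduled scan. At the second scheduled scan it is 116 to 133 days if scan windows run from allocation, or 109 to 140 days if they run from the previous scan. These ranges assume scheduled imaging and first dose within 3 days of allocation. The illustrated effect on a median further assumes that the cited 6.3 months was measured from response.

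Section 4.2.3.1 also contradicts Section 8.2.2 on the population, and it leaves out death. The protocol fixes the definition itself, so this is not a detail left to a separate analysis plan. It should be corrected, but it affects one descriptive secondary endpoint and leaves the primary response rate, the interim rule and the sample size untouched.

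**What to change.** Put one definition in Sections 4.2.3.1 and 8.2.2: in patients with CR or PR, DOR is the time from the first documented CR or PR to the first RECIST 1.1 progression or death from any cause, whichever occurs first. Remove SD from the DOR text in Section 4.2.3.1. If a measure covering CR, PR and SD is wanted, report it separately as duration of disease control, where a start at first dose is workable.

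The cost is wording in two sections. The date of first response comes from RECIST 1.1 assessments already scheduled, so no new data are needed. The reported DOR will be shorter, which is a reason to make the change before results are known.

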### **8.3 Study population**

All patients screened and enrolled will be accounted for. All enrolled discontinuations will be summarized by reason for discontinuation. The number of patients screened and enrolled will be presented.

### **8.4 Sample size determination**

The Simon minimax 2 stage design will be used in this study. The response rate to pembrolizumab in unselected breast cancer is estimated to be 10%. We hypothesize that the response rate to pembrolizumab in patients with APOBEC3B germline deletion will be 25%. Assuming power of 80% and one-sided level of significance of 5%, 22 evaluable patients will be required in stage I. If 6 or more patients achieve CR/PR in stage I, the study will proceed to stage II to enroll another 18 patients (total 40 evaluable patients). Taking into account an estimated 10% attrition rate, we plan to enroll 44 patients to have 40 patients evaluable for response.

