## 8.6 Interim Analysis

There will be one interim analysis at the end of Stage I (Section 8.4). If 6 or more patients out of the 22 evaluable patients achieve CR/PR in stage I, the study will proceed to stage II to enroll another 18 patients (total 40 evaluable patients).

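### The stage I rule of 6 or more responders in 22 does not belong to the stated Simon minimax design and caps power at 48%, not 80%

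*Protocol*

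**What the plan says.** Protocol section 8.4 names the design: "The Simon minimax 2 stage design will be used in this study". It takes 10% as the response rate in unselected breast cancer and 25% as the hypothesised rate in carriers of the deletion. It then sets the error rates and the first-stage size: "Assuming power of 80% and one-sided level of significance of 5%, 22 evaluable patients will be required in stage I". The rule for opening stage II is "If 6 or more patients achieve CR/PR in stage I, the study will proceed to stage II to enroll another 18 patients", which gives "total 40 evaluable patients".

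Section 8.6 makes this the only interim analysis and repeats the rule with its denominator: "If 6 or more patients out of the 22 evaluable patients achieve CR/PR in stage I, the study will proceed to stage II".

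Neither section gives the number of responders out of 40 needed to declare activity. That may stand in a separate analysis plan and is not the point here.

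**The concern.** Six of 22 is 27.3%, above the 25% that the trial hopes to find. A futility boundary normally lies between the null and target rates, so that a treatment performing as hoped almost always passes. A boundary above the target rate will stop such a treatment about half the time, which cannot be squared with 80% power.

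This is the trial's only go/no-go rule, and both sections state it the same way, so it would be applied as written. If the hypothesis is exactly true, the trial could easily end after 22 patients with a negative conclusion, while readers of the protocol were told that the chance of missing a real effect was 20%.

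**Working it through.** **Inputs**, all from section 8.4: p0 = 0.10, p1 = 0.25, one-sided alpha 0.05, power 0.80, n1 = 22, n2 = 18, N = 40, continue if X1 ≥ 6. X1 is the number of responders in stage I and X2 the number in stage II.

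**Formulas.** With X1 ~ Bin(22, p) and X2 ~ Bin(18, p) independent, continuation at c or more and success at s or more of 40:

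- P(continue) = P(X1 ≥ c)
- P(declare activity) = Σ over x ≥ c of P(X1 = x) · P(X2 ≥ s − x)
- Expected N = 22 + 18 · P(X1 ≥ c)

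The second formula gives alpha at p0 and power at p1. Since success requires continuation, P(declare activity) ≤ P(X1 ≥ c) for every s.

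**Step 1: reproduce the plan's sizes.** An exhaustive exact search over all two-stage designs with alpha ≤ 0.05 and power ≥ 0.80 finds none with N below 40. Among designs with N = 40, the smallest expected N under p0 occurs at n1 = 22. So 22 + 18 = 40 is reproduced exactly. That design stops with 2 or fewer of 22, continues with 3 or more, and succeeds with 8 or more of 40. Its alpha is 0.0398 and its power 0.8032.

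**Step 2: power ceiling under the written rule.** At p = 0.25 the probabilities of 0 to 5 responders in 22 are 0.0018, 0.0131, 0.0458, 0.1017, 0.1611 and 0.1933, which sum to 0.517. Hence P(X1 ≥ 6) = 1 − 0.517 = 0.483. No final boundary can lift power above this figure.

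Outcomes of 3, 4 or 5 responders have total probability 0.1017 + 0.1611 + 0.1933 = 0.456. These are the cases in which the stated design continues and the written rule does not.

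**Step 3: the two rules compared**, both with success at 8 or more of 40:

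| | Continue at ≥ 3 of 22 | Continue at ≥ 6 of 22 |
|---|---|---|
| P(continue), true rate 25% | 0.939 | 0.483 |
| Power at 25% | 0.803 | 0.475 |
| P(end at stage I), true rate 10% | 0.620 | 0.982 |
| P(continue), true rate 10% | 0.380 | 0.018 |
| Type I error | 0.040 | 0.012 |
| Expected N at 10% | 28.8 | 22.3 |

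**Step 4: is there another reading?**

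- With n1 = 22 and N = 40, the stated alpha and power hold together only for continuation at 1, 2 or 3 or more, with success at 8 or more of 40. Of these, 3 or more has the smallest expected N under p0.
- Alpha 0.025 gives boundaries of 2/23 and 9/49. Power 90% gives 3/31 and 9/55. Neither has 22 patients in stage I or a first-stage boundary near 6.
- Reading the rule as more than 6 lowers the ceiling to 0.301.
- With 6 or more of 22, an 80% chance even of reaching stage II needs a true rate of about 34%.

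**The case against.** Four points can be made for the plan.

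1. **The rule may be a deliberately strict gate.** A sponsor may reasonably want a high hurdle before treating 18 more patients. The document does not show whether 6 is a slip or a choice. But nothing in it says that the gate was tightened, and the 80% power is stated for the design with this rule. A deliberate gate would still leave the power statement wrong.

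2. **A separate analysis plan could complete the design.** It could supply the final boundary, but that cannot help: the 48.3% ceiling comes from stage I alone and applies to every final boundary.

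3. **Stopping is not written out.** Sections 8.4 and 8.6 say when stage II opens, not what happens with 5 or fewer responders, and the termination criteria in section 5.6 do not list a failed stage I. Stopping is therefore inferred from the named Simon design and from the condition placed on stage II. The inference is sound, but it is an inference.

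4. **The error is on the safe side for false positives.** This stands. Type I error under the written rule is at most 0.018, so a positive result would remain valid. The harm is confined to loss of power, and a 0.517 chance of ending early is only slightly worse than a coin toss. It ends this trial's test of the hypothesis and does not settle the value of the drug.

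None of these removes the contradiction between the threshold and the stated power.

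**Conclusion.** The concern holds. The sizes of 22 and 40 are those of the stated minimax design, but the threshold of 6 is not; the stated inputs give 3. As written, power at a true rate of 25% is at most 48.3%, and 47.5% with success at 8 or more of 40, against the claimed 80%.

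The result uses only the protocol's figures and exact binomial probabilities. It assumes independent responses at a common rate, exactly 22 and 40 evaluable patients, and that failing the stage I rule ends the trial. The 47.5% also assumes the minimax final boundary; the 48.3% ceiling does not.

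**What to change.** In sections 8.4 and 8.6, replace 6 with 3, so that stage II opens with 3 or more responders among the first 22 evaluable patients, and say that the trial stops otherwise. It would help to state the matching final boundary (8 or more of 40) and the exact operating characteristics in the same place: alpha 0.040, power 0.803 and probability of early stopping under the null 0.62. The final boundary could equally sit in the analysis plan.

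If 6 of 22 is intended, keep it, but no longer describe the design as Simon minimax with 80% power. State that power at 25% is at most 48%, and give the exact figure for the final boundary chosen.

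The cost is a short amendment to two sections, with no patients beyond the planned 40. The price of moving to 3 is that an inactive drug would reach stage II with probability 0.38 instead of 0.02, raising expected N under the null from 22.3 to 28.8. The stated design already accepts this.

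Timing matters. The trial is open label, so the change must be made and dated before stage I responses are examined. If they are already known, lowering the threshold is a data-dependent change and must be reported as such.

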## 8.5 Analysis population

The Full Analysis Set (FAS) population will serve as the primary population for the analysis of efficacy data in this study. The FAS population consists of all subjects who:

- Receive at least one dose of study treatment, and
- Have a baseline scan with measurable disease per RECIST 1.1

## 8.6 Interim Analysis

There will be one interim analysis at the end of Stage I (Section 8.4). If 6 or more patients out of the 22 evaluable patients achieve CR/PR in stage I, the study will proceed to stage II to enroll another 18 patients (total 40 evaluable patients).

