### **5.5 Participant Replacement Strategy**

Additional patients will be recruited to meet the samples size required

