- g. After Cycle 1, laboratory samples can be collected up to 72 hours prior to the scheduled time point. CBC with differential, chemistry panel and liver panel to be performed every cycle. Details can be found in Section 7.1.3 Laboratory Procedure/Assessments. Liver panel to include albumin, ALT, AST, total bilirubin, alkaline phosphatase and total protein.
- h. While on treatment, PT/INR and aPTT, UA and thyroid function tests will be performed every other cycle.
- i. Screening tumour imaging will be performed within 28 days prior to treatment allocation. Imaging at screening should include chest, abdomen, and pelvis. The first on-study imaging time point will be performed at 9 week ( $\pm 7$  days) calculated from the date of treatment allocation and will be continue to be performed Q9W ( $63\pm 7$  days) in the first year, Q12W ( $84\pm 7$ days) in the second year of therapy.
- j. If previous imaging was obtained within 4 weeks prior to the date of discontinuation, then imaging at treatment discontinuation is not mandatory.
- k. Only for those with a history of bone metastases, to be repeated Q9W ( $63\pm 7$  days) from treatment allocation in first year, Q12W ( $84\pm 7$ days) in second year of therapy.
- l. Only for those with known brain metastases, CT or MRI brain to be repeated Q9W ( $63\pm 7$  days) from treatment allocation in first year, Q12W ( $84\pm 7$ days) in second year of therapy.
- m. Blood for correlative studies should be collected at Cycle 3, at Cycle 6 and again at discontinuation (end of treatment).
- n. Tissue collection through core needle biopsy (CNB) or excisional biopsy (EB) may be performed when progressive disease is confirmed.

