#### **7.1.2.6 Tumour Imaging and Assessment of Disease**

Tumour imaging is strongly preferred to be acquired by computed tomography (CT). For the abdomen and pelvis, contrast-enhanced magnetic resonance imaging (MRI) may be used when CT with iodinated contrast is contraindicated, or when local practice mandates it. MRI is the preferred modality for imaging the brain. The same imaging technique regarding modality, ideally the same scanner, and the use of contrast should be used in a participant throughout the study to optimize the reproducibility of the assessment of existing and new tumour burden and improve the accuracy of the assessment of response or progression based on imaging.

Expedited confirmation of measurable disease based on RECIST 1.1 at screening should be used to determine participant eligibility. Confirmation that the participant's imaging shows at least 1 lesion that is appropriate for selection as a target lesion per RECIST 1.1 is highly recommended prior to participant allocation.

Participant eligibility will be determined using local assessment (Investigator assessment) based on RECIST 1.1. In addition, images (including via other modalities) that are obtained at an unscheduled time point to determine disease progression, as well as imaging obtained for other reasons, but which demonstrate radiologic progression, should also be used to determine progression.

When the Investigator identifies radiographic progression per RECIST 1.1, efforts should be made to verify radiologic PD. Treatment should continue until PD has been verified. Regardless of whether PD is verified, if the Investigator considers the participant has progressed, but elects to implement iRECIST, the Investigator will assess for confirmation of progression by iRECIST at subsequent time points.

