#### **7.1.2.6.3 End of Treatment and Follow-up Tumour Imaging**

In participants who discontinue study treatment, tumour imaging should be performed at the time of treatment discontinuation ( $\pm 4$  week window). If previous imaging was obtained within 4 weeks prior to the date of discontinuation, then imaging at treatment discontinuation is not mandatory. In participants who discontinue study treatment due to documented disease progression and the Investigator elects not to implement iRECIST, this is the final required tumour imaging.

In participants who discontinue study treatment without documented disease progression, every effort should be made to continue monitoring their disease status by tumour imaging using the same imaging schedule used while on treatment (every 9 weeks in Year 1 or every 12 weeks after Year 1) to monitor disease status until the start of a new anticancer treatment, disease progression, pregnancy, death, withdrawal of consent, or the end of the study, whichever occurs first.

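### Does counting the stage I gate in evaluable patients, while ORR is analysed on the FAS, call for a change?

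*Protocol*

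**What the plan says.** Protocol 8.4 describes a Simon minimax two-stage design with a null ORR of 10%, a target of 25%, one-sided 5% significance and 80% power. It needs 22 evaluable patients in stage I and 40 in total. On enrolment it says "we plan to enroll 44 patients to have 40 patients evaluable for response", allowing for 10% attrition. Section 8.6 repeats the gate: the trial goes on "If 6 or more patients out of the 22 evaluable patients achieve CR/PR in stage I".

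Section 8.5 states: "The Full Analysis Set (FAS) population will serve as the primary population for the analysis of efficacy data in this study". Membership requires one dose and a baseline scan with measurable disease. A post-baseline scan is not required. Section 8.2.1 defines ORR as a proportion of the analysis population.

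Section 5.5 reads in full: "Additional patients will be recruited to meet the samples size required". No section defines evaluable, equates it with the FAS or separates it from the FAS.

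**The concern.** Two different terms, one section apart, govern the go/no-go count and the primary estimate. If evaluable means having a post-baseline assessment, a treated patient who is lost before any scan drops out of the 22, may be replaced under 5.5, and still counts as a non-responder in the FAS. The gate would then rest on a set selected partly on outcome.

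The error would run one way. An unscanned patient has no recorded response, so the first 22 evaluable patients contain every responder among the first 22 FAS patients. The evaluable count can therefore only make proceeding more likely.

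The text seems to leave room for such patients. On scans at discontinuation, 7.1.2.6.3 says "If previous imaging was obtained within 4 weeks prior to the date of discontinuation, then imaging at treatment discontinuation is not mandatory". Flow chart 6.1 says "Screening tumour imaging will be performed within 28 days prior to treatment allocation". For someone who stops soon after the first dose, the screening scan could therefore meet the exemption. Measurable disease is also an entry criterion (5.1.1), and dosing follows allocation within 3 days (Table 1), so few allocated patients would miss the FAS. That makes 10% attrition look more like loss after dosing.

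**Working it through.** **Plan's own figures.** An exact search for the minimax design with the inputs of 8.4 returns 22 in stage I and 40 in total, as printed (type I error 0.0398, power 0.803). Enrolment: 40 × 1.1 = 44. That search gives a stage I gate of 3, not 6. This is a separate matter and carries no weight here; the figures below use the gate as printed.

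**Effect of the two readings on the gate.** Let p be the true ORR in the FAS and f the fraction of treated patients who are unscanned and replaced. The rate among evaluable patients is p/(1 − f), and the chance of passing is P(X ≥ 6) for X binomial with n = 22 and that rate. The documents do not give f. The value 10% assigns all the stated attrition to this group and is an upper bound.

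| f | p/(1 − f), p = 10% | P(pass) | p/(1 − f), p = 25% | P(pass) |
|---|---|---|---|---|
| 0 (FAS count) | 10.0% | 0.0182 | 25.0% | 0.4832 |
| 1% | 10.1% | 0.0191 | 25.3% | 0.4942 |
| 2.5% | 10.3% | 0.0204 | 25.6% | 0.5112 |
| 5% | 10.5% | 0.0230 | 26.3% | 0.5402 |
| 10% | 11.1% | 0.0292 | 27.8% | 0.6011 |

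Because the error is one-way, the difference from the first row is the share of trials in which the two counts give opposite decisions. For f = 1%, 2.5%, 5% and 10% this is:

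- at p = 10%: 0.1, 0.2, 0.5 and 1.1 percentage points;
- at p = 25%: 1.1, 2.8, 5.7 and 11.8 percentage points.

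**Type I error.** A false positive requires passing the gate, so it cannot exceed 2.9% even at f = 10%, whatever the final cut-off.

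**Estimate.** With 23 treated, 1 unscanned and 6 responders, the gate sees 6/22 = 27.3% and the FAS gives 6/23 = 26.1%. The reported ORR is the second figure on either reading.

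**Who could be unscanned.** Three provisions bear on this.

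- The exemption in 7.1.2.6.3 removes only the discontinuation scan. The next paragraph of that section, and 7.1.5.3.2, keep patients who stop without documented progression on the 9-week imaging schedule.
- Section 7.1.2.6 also uses images "that are obtained at an unscheduled time point to determine disease progression".
- What remains is mainly death, withdrawal of consent or new anticancer therapy before the first scan, in patients who entered with ECOG 0 or 1 and a life expectancy of at least 3 months (5.1.1).

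**Whether attrition must follow dosing.** Section 7.1.1.6 gives an allocation number to every consented subject. The trial summary counts participation from consent, with up to 28 days of screening. If enrolment is counted from there, loss between consent and first dose could make up the whole 10%, and the evaluable set and the FAS would coincide.

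**The case for a change.** The strongest case for a change is that this is not simply a matter for an unseen SAP. Section 8 itself fixes both the FAS and the gate, and a stage rule governs conduct, so the sponsor has to know who counts before stage I closes. An undefined term could be settled after the data are seen. At f = 2.5% the chance that at least one of the first 22 treated patients is unscanned is 1 − 0.975^22 = 43%. The repair would take a sentence each in 5.5, 8.4 and 8.6 and no extra patients.

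Part of this stands. The term is undefined, 5.5 is silent on who may be replaced, and the unscanned group cannot be shown to be empty. But one unscanned patient changes the decision only when the responder count is at the boundary, which is why 43% shrinks to 2.8 points at a 25% ORR.

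The repair also has a price. Under the same assumptions it removes 0.2 to 1.1 points of wrong decisions to proceed and 2.8 to 11.8 points of right ones. Nor is the FAS plainly the matching denominator. Some response rates cited in the rationale are in evaluable patients (18.5% of 27 in 4.2.1.1; 12% of 25 in 4.2.1.2), though the 4.7% in 4.2.1.1 is out of all 170 enrolled in its cohort.

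**Conclusion.** No change is needed. The protocol leaves a term undefined but does not contradict itself. Section 8.5 names the FAS for efficacy data without limiting this to the final analysis, so a statistician counting stage I responses has a natural default. On that reading the gate and the primary analysis use the same patients.

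On the other reading, the effect is confined to the decision to proceed: 0.2 to at most 1.1 points at a true ORR of 10%, and 2.8 to at most 11.8 points at 25%, for f from 2.5% to 10%. These sizes assume that every unscanned patient is replaced. They also rest on a value of f that the documents do not supply and that continued imaging after early discontinuation should keep small. The primary ORR is on the FAS either way, and type I error stays below 5% under the printed gate. What is left is a missing definition that analysts can supply sensibly, together with a choice of denominator on which reasonable statisticians differ.
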